12. DATA REPORTING / REGULATORY REQUIREMENTS

Adverse event lists, guidelines, and instructions for AE reporting can be found in Section 7.

12.1 Data Reporting

Data collection for this study will be done exclusively through Medidata Rave. Access to the trial in Rave is granted through the iMedidata application to all persons with the appropriate roles assigned in the Regulatory Support System (RSS). To access Rave via iMedidata, the site user must have an active CTEP IAM account (https://ctepcore.nci.nih.gov/iam) and the appropriate Rave role (Rave CRA, Read-Only, or Site Investigator) on either the Corresponding Organization or Participating Organization roster at the enrolling site.

Upon initial site registration approval for the study in RSS, all persons with Rave roles assigned on the appropriate roster will be sent a study invitation e-mail from iMedidata. To accept the invitation, site users must log into the Select Login (https://login.imedidata.com/selectlogin) using their CTEP-IAM user name and password, and click on the "accept" link in the upper right-corner of the iMedidata page. Please note, site users will not be able to access the study in Rave until all required Medidata and study specific trainings are completed. Training will be in the form of electronic learnings (eLearnings), and can be accessed by clicking on the link in the upper right pane of the iMedidata screen.

Users that have not previously activated their iMedidata/Rave account at the time of initial site registration approval for the study in RSS will also receive a separate invitation from iMedidata to activate their account. Account activation instructions are located on the CTSU website, Rave tab under the Rave resource materials (Medidata Account Activation and Study Invitation Acceptance). Additional information on iMedidata/Rave is available on the CTSU members' website under the Rave tab or by contacting the CTSU Help Desk at [name] or by e-mail at [contact].

12.1.1 Method

This study will be monitored by the Clinical Trials Monitoring Service (CTMS). Data will be submitted to CTMS at least once every two weeks via Medidata Rave (or other modality if approved by CTEP). Information on CTMS reporting is available at http://www.theradex.com/CTMS. On-site audits will be conducted three times annually (one annual site visit and two data audits). For CTMS monitored studies, after users have activated their accounts, please contact the Theradex Help Desk at [contact] or by email at [contact] for additional support with Rave and completion of CRFs.

12.2 NIH Required Data Safety and Monitoring Plan

The investigators at each participating center will be responsible for the collection, maintenance, and quality control of the study data. Adverse events observed in patients enrolled on the trial will be monitored in real time by the Principal and Associate Investigators, and attribution of these events to the research will be determined at the end of each treatment cycle in each subject. The clinical research team (PI, associate investigators, research nurses, data managers) will meet weekly when patients are being actively treated on the trial to discuss each patient in detail and ensure that all events are graded appropriately, and that the attribution to study drug is correct.

The Coordinating Center is responsible for establishing conference calls between participating sites at least on a monthly basis to discuss the observed toxicities and protocol issues.

All SAEs will be reported through CTEP-AERS to CTEP, to the Coordinating Center PI at NCI, and forwarded to the IRB per Section 7. In all cases where the dose of the study treatment has been reduced/modified or the patient withdrawn due to unusual or unusually severe toxicity considered related to the study treatment, the investigator must contact and inform the Coordinating Center PI. All sites will be monitored by the CTEP drug monitor, who will receive data from all participating sites.

Data will be monitored regularly by the PI in order to identify significant toxicity trends. Any new significant finding that may affect the patient's willingness to continue in the study will be shared with patients.

Confidentiality will be maintained as much as possible, consistent with applicable regulations. Names of participants or identifying material will not be released without patient permission, except when such release is required by law. No patient's name or identifying information will be released in any publication or presentation. Records are maintained according to current legal requirements, and are made available for review according to the requirements of the FDA or other authorized user, only under guidelines established by the Federal Privacy Act.

Safety Monitoring Committee:

Because this is a multi-institutional protocol for which the NCI CCR is the Coordinating Center, it will be monitored by the DTC Safety Monitoring Committee, NCI.

12.3 Multicenter Guidelines

This protocol will open initially at the NCI. The NIH IRB will be notified once the participating centers' IRBs have approved the studies to open. This protocol will follow the CCR's Clinical Research Operations' SOPs for multicenter trials.

12.3.1 IRB Approvals

As the Coordinating Center for a trial, it is the PI's responsibility to ascertain that no patients are entered on the trial at a participating institution without full IRB approval. Thus, the NIH IRB must approve the addition of each participating institution to the protocol and will require a copy of the local IRB approval from each participating institution before NIH IRB approval will be granted.

The PI will provide the NIH IRB with a copy of the participating institution's approved yearly continuing review. Registration will be halted at any participating institution in which a current continuing approval is not on file at the NIH IRB.

12.3.2 Amendments and Consents

The NCI PI will provide the NIH IRB with copies of all amendments, consents, and approvals from each participating institution.

12.3.3 Data Collection

The investigators will be responsible for the collection, maintenance, and quality control of the study data. Each site investigator is also responsible for maintaining all source documentation related to the study, including any films, tracings, computer discs or tapes. NCI will be responsible for data management, data analysis, and reporting. Data collection forms will be provided to the participating institutions. Required data include, not exclusively: prior disease-related therapies with dates, disease type, stage, disease sites, with measurements, and concurrent medications.

12.3.4 Human Data Sharing Plan

What data will be shared?

We will share human data generated in this research for future research as follows:

x De-identified data in an NIH-funded or approved public repository

x Identified data in BTRIS (automatic for activities in the NIH Clinical Center)

x De-identified or identified data with approved outside collaborators under appropriate agreements

How and where will the data be shared?

Data will be shared through:

x An NIH-funded or approved public repository: clinicaltrials.gov

x BTRIS (automatic for activities in the NIH Clinical Center)

x Approved outside collaborators under appropriate individual agreements

x Publication and/or public presentations

When will the data be shared?

x At the time of publication or shortly thereafter

12.3.5 Data and Center Audits

Audits will be conducted yearly to ensure data integrity and provide quality control. These audits will be conducted by the NCI research team. Selected patient charts should be audited as well as the participating institution's Standard Operating Procedures (SOP) at the time of the visit. Data from participating institutions should be available when the protocol is audited at the NCI.

12.4 CTEP Multicenter Guidelines

This protocol will adhere to the policies and requirements of the CTEP Multicenter Guidelines. The specific responsibilities of the Principal Investigator and the Coordinating Center (Study Coordinator) and the procedures for auditing are presented in Appendix B.

- The Principal Investigator/Coordinating Center is responsible for distributing all IND Action Letters or Safety Reports received from CTEP to all participating institutions for submission to their individual IRBs for action as required.
- Except in very unusual circumstances, each participating institution will order DCTDsupplied agents directly from CTEP. Agents may be ordered by a participating site only

after the initial IRB approval for the site has been forwarded by the Coordinating Center to the CTEP PIO ([contact]) (except for Group studies).

12.5 Collaborative Agreements Language

N/A

13. STATISTICAL CONSIDERATIONS

13.1 Study Design/Endpoints

The primary objective of this trial is to establish the safety, tolerability, and MTD of LMP744 administered intravenously daily for 5 days in 28-day cycles, to patients with refractory solid tumors. This study will follow design 3 of the Simon accelerated titration designs (26), with dose escalation proceeding in 1-patient cohorts and switching to standard 3+3 dose escalation of dose levels when specific criteria are met (Section 5.1.1). (*Note: As of Amendment G* [10/18/18], the study switched to standard 3+3 dose escalation. As of Amendment I [9/25/19], there is flexibility to accrue up to an additional 3 patients on any dose level that has 1 DLT observed among 6 patients [see Section 5.1.2.1]. As of Amendment L [date 6/7/2021], the MTD has been identified and the expansion cohort will begin accrual [see Section 5.1.2.2].)

Following this, another 15 patients will be treated at the MTD on an expansion cohort, which will include mandatory biopsies. With 15 patients and a tumor biopsy QA criteria failure rate of 50% with respect to paired (pre- and post-dose) biopsies, we have an 85% likelihood of having at least 6 usable PD samples, and 95% likelihood of having at least 5 usable samples from the expansion cohort. Biopsy tissue quality will be monitored and accrual to the expansion phase will stop once we have obtained 6 usable paired samples. With 6 PD sample pairs, there is 90% power to detect a treatment effect equivalent to 1.85 SD's (associated with the intra-patient baseline variability of the PD marker) with the paired 2-sample T-test, at the 1-sided .05 significance level, for a given PD variable of interest. PD variables may be log-transformed to achieve more nearly normal distributions.

DLTs will be summarized descriptively according to dose level. In addition, the relation of dose level with presence or absence of DLT will be analyzed using logistic regression, as described by Simon (20).

All AEs will be tabulated by type and grade according to dose level. In addition, the presence or absence of grade 2 or higher toxicity for each patient in each treatment cycle will be modeled using random effects logistic regression as described by Simon (20), incorporating dose during the cycle and total dose for previous cycles, with intra-patient random effects.

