5.1.2.2 Expansion Cohort

Once the MTD is identified, another 15 patients will be treated at the MTD on an expansion cohort. With 15 patients and a biopsy QA failure rate of 50% with respect to paired biopsies, there is an 85% likelihood of having at least 6 usable samples and a 95% likelihood of having at least 5 usable samples.

With Amendment L (date 6/7/2021), the MTD is identified as dose level 6 (190 mg/m²/day) and the expansion cohort will begin accrual.

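### Section 13.1's only power statement does not reproduce: six pairs give about 86% power at 1.85 intra-patient SDs, not 90%

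*Combined protocol and SAP*

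**What the plan says.** Section 13.1 plans 15 patients in an expansion cohort with mandatory biopsies, assumes that half of the paired biopsies fail quality control, and stops accrual once six usable pairs are in hand. The power statement follows directly: "With 6 PD sample pairs, there is 90% power to detect a treatment effect equivalent to 1.85" SDs. The SD is described as "associated with the intra-patient baseline variability of the PD marker", the test is named in "with the paired 2-sample T-test", and the error rate is set "at the 1-sided .05 significance level, for a given PD variable of interest".

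The same section gives the expected yield as "85% likelihood of having at least 6 usable PD samples, and 95% likelihood of having at least 5 usable samples". Section 5.1.2.2 repeats it: "there is an 85% likelihood of having at least 6 usable samples and a 95% likelihood of having at least 5 usable samples".

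No other power calculation appears in the document. Section 13.3 says that exploratory evaluations carry no formal multiplicity adjustment, so the 0.05 level applies to each marker separately.

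**The concern.** Every input to the calculation is stated (pairs, effect, SD unit, test, sidedness, level), so the 90% can be checked without outside information. It looked too high for a t-test with 5 degrees of freedom when the effect is scaled to the within-patient SD of one measurement rather than to the SD of the difference.

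At stake is the only quantitative support given for six pairs as a sufficient number of paired biopsies. A reader who relies on it would put the chance of missing a 1.85-SD marker change at 10%. The text also leaves the SD open to two readings, and these differ by about 12 percentage points of power.

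**Working it through.** **Inputs (Section 13.1).** n = 6 pairs; effect δ = 1.85σ, with σ the intra-patient SD of the marker; paired t-test; one-sided α = 0.05. The SD of a post-minus-pre difference is not given. With two independent measurements and the same treatment effect in every patient, it is σ√2.

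**Formula.** Power = P(T > t_crit), where T is noncentral t with n − 1 degrees of freedom and noncentrality λ = (δ / SD_diff) × √n.

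**The plan's 90%, tried on the named test.**
- df = 5 and t_crit = 2.015.
- λ = (1.85 / √2) × √6 = 1.308 × 2.449 = 3.204.
- Power = **86.3%**. A simulation of 1,000,000 trials also gave 86.3%.
- Type II error = 100 − 86.3 = 13.7%.

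**Effect needed for 90%.** Solving for the standardised difference gives 1.40 SDs of the paired difference. In intra-patient units this is 1.401 × √2 = **1.98**. Relative to the stated effect, 1.98 / 1.85 = 1.07, or 7% larger.

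**Other ways of reaching 90% at 1.85 with six pairs, one-sided 0.05.**

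| Reading | Power at 1.85 | Effect for 90% |
|---|---|---|
| Paired t, 5 df, SD of a single measurement (as named) | 86.3% | 1.98 |
| Paired t, 5 df, SD of the difference (λ = 1.85 × √6 = 4.53) | 98.6% | 1.40 |
| Unpaired two-sample t, 6 per group, 10 df | 90.9% | 1.82 |
| t critical value (5 df) with normal-approximation power | 88.3% | 1.90 |
| Normal approximation throughout | 94.1% | 1.69 |

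The unpaired test with 10 degrees of freedom comes closest, but it is not the planned test and does not match exactly. That it was the source of the 90% is only an inference.

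**Number of pairs.** On the reading as named, power at 1.85σ is 77.4% with 5 pairs and 91.8% with 7.

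**Yield figures, Binomial(15, 0.5).**
- P(at least 6) = 27,824 / 32,768 = 84.9%. The stated 85% is right.
- P(at least 5) = 30,827 / 32,768 = 94.1%. The stated 95% is slightly high.

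**Power averaged over the yield, capped at six pairs.** The chances of exactly 5, 4, 3 and 2 usable pairs are 0.0916, 0.0417, 0.0139 and 0.0032. The matching powers are 0.774, 0.638, 0.447 and 0.229. With fewer than two pairs no test is possible, and power is counted as zero. Then 0.849 × 0.863 + 0.0916 × 0.774 + 0.0417 × 0.638 + 0.0139 × 0.447 + 0.0032 × 0.229 ≈ **83.7%**.

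**The case against.** The strongest reply is that 86.3% depends on a step the protocol does not spell out. If pre- and post-dose errors within a patient are correlated, SD_diff = σ√(2(1 − ρ)). Power reaches 90% when SD_diff is about 1.32σ, which needs ρ = 1 − 1.3205² / 2 ≈ 0.13. That is a modest correlation, and on the paired-difference reading the statement is even conservative. This stands as a reason to define the SD. It does not rescue the figure, because the document gives no such correlation and √2 is the ordinary consequence of the unit it names.

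The second reply concerns consequences, and much of it stands. The PD markers are exploratory (Section 1.3), results are to be reported with caveats (Section 13.3), and no go/no-go rule depends on the t-test. The cohort of 15 is tied to biopsy yield, not to power, and the text never says outright that 90% power is why six was chosen. The power statement simply follows the six-pair rule and is the only support offered for it.

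Third, the power sentence is conditional on six pairs, and the plan discloses that six may not be reached. The 77.4% and 83.7% figures are therefore useful context, not contradictions of the plan. The 94.1% against 95% is minor, particularly beside the uncertainty in the assumed 50% failure rate.

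**Conclusion.** The stated power is wrong as written. With the test, level, number of pairs and SD unit that Section 13.1 names, power at 1.85 intra-patient SDs is 86.3%, a shortfall of 3.7 percentage points. The effect detectable with 90% power is 1.98 intra-patient SDs. Reading the SD as that of the paired difference gives 98.6%, so that reading does not restore 90% either.

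The 86.3% assumes independent errors in the two measurements and the same treatment effect in every patient. Positive error correlation would raise it; variation in the effect between patients would lower it. The mistake is small, confined to an exploratory endpoint, and has no bearing on the MTD or on safety. It should still be corrected, because it is the plan's only power statement and its unit is ambiguous.

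**What to change.** In Section 13.1, replace the power sentence with wording such as: With 6 pairs, the one-sided 0.05 paired t-test has 86% power at 1.85 intra-patient SDs (90% at 1.98, equivalently 1.40 SDs of the paired difference); with 5 pairs, power at 1.85 is 77%. State that the SD is the within-patient SD of a single measurement, and that the figures assume independent errors and a constant treatment effect. If the sponsor meant a different SD, name it and recompute.

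In Sections 13.1 and 5.1.2.2, change 95% to 94%.

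The cost is a few sentences and a slightly less favourable stated power. Enrolment, the number of biopsies and the analysis are unchanged.

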13.2 Sample Size/Accrual Rate

As of Amendment G (10/18/18), if all dose levels are evaluated, we anticipate enrolling a minimum of 35 patients and a maximum of 47 patients. In order to allow for a small number of patients who may not be evaluable, the accrual ceiling for this trial is set at 53 patients.

It is anticipated that 1 patient may be enrolled per month onto this study during the accelerated titration stage (already completed) and 1-2 patients/month thereafter. It is expected that 25-35 months will be required to accrue the number of patients necessary to complete the trial.

13.3 Analysis of Secondary and Exploratory Endpoints

Exploratory evaluations will be performed, with results reported with appropriate caveats about the exploratory nature of the analysis, and without formal adjustment for multiple comparisons.

14. HUMAN SUBJECTS PROTECTION

14.1 Rationale for Subject Selection

This study will be open to all individuals regardless of gender, ethnicity, or race provided that the aforementioned inclusion and exclusion criteria are met. For safety reasons, pregnant women and children are excluded from this study. The NCI is the coordinating center for this multi-institutional study. This study will be recruited through internal referral, our physician referral base, and through various cancer information hotlines (i.e., Clinical Studies Support Center, [name].) Participants should realize that there is no guarantee of benefit to them from participation in this trial. The results of this trial may benefit future cancer patients. To date, there is no information that suggests that differences in drug metabolism or effect on tumor would be expected in one ethnic group compared to another. Efforts will be made to extend accrual to each representative population, but a balance must be struck between participant safety considerations and limitations on the number of individuals exposed to potentially ineffective treatments on the one hand and the need to explore racial/ethnic aspects of clinical research on the other hand. If differences in outcome that correlate to ethnic identity are noted, a follow-up study may be written to investigate those differences more fully.

Inclusion of Women and Minorities:

This study will be open to all individuals regardless of gender, ethnicity, or race provided that the aforementioned inclusion and exclusion criteria are met.

| Racial Categories | Not Hispanic or Latino | | His | panic or Latino | Total |
|--|------------------------|------|--------|-----------------|-------|
| | Female | Male | Female | Male | |
| American Indian/ Alaska Native | 1 | 0 | 0 | 0 | 1 |
| Asian | 2 | 3 | 0 | 0 | 5 |
| Native Hawaiian or Other Pacific Islander | 1 | 1 | 0 | 0 | 2 |
| Black or African American | 7 | 7 | 1 | 0 | 15 |
| White | 12 | 13 | 2 | 2 | 29 |
| More Than One Race | 0 | 1 | 0 | 0 | 1 |
| Total | 23 | 25 | 3 | 2 | 53 |

14.2 Justification for Exclusions

Due to lack of knowledge on the effects of LMP744 on the fetus or infants, as well as the possibility of teratogenic effects, pregnant and nursing women will be excluded from this trial. Participants with unstable or serious medical conditions are due to the possibility that the underlying condition may obscure the attribution of adverse events to study drug.

14.3 Participation of Children

Participants under the age of 18 will be excluded from study because no dosing or adverse event data are currently available for the use of LMP744 in participants <18 years of age.

14.4 Evaluation of Benefits and Risks/Discomforts

There may or may not be any clinical benefit to a patient from participation in this trial. Their participation will benefit future cancer patients. Potential risks include the possible occurrence of any of a range of side effects that are listed in the consent document. The procedure for protecting against or minimizing risks will be to medically evaluate patients as described in Section 10. Although no compensation is available, any injury will be fully evaluated and treated in keeping with the benefits or care to which participants are entitled under applicable regulations.

14.4.1 Procedure for Protecting Against or Minimizing Any Potential Risks

All care will be taken to minimize side effects, but they can be unpredictable in nature and severity. This study may involve risks to patients, which are currently unforeseeable. All patients will be monitored for side effects from taking study medication and from undergoing biopsy and blood sampling procedures.

14.4.2 Radiation Risks

As biopsies will be performed with CT guidance, this research study involves exposure to radiation from up to 2 CT scans solely for research purposes with a combined effective dose of 1.6 rem. This is below the guideline of 5.0 rem per year allowed for research subjects by the NIH Radiation Safety Committee.

14.5 Consent and Assent Process and Documentation

An associate or principal investigator on the trial will inform patients of the purpose, alternatives, drug administration plan, research objectives, and follow-up of this trial. The patient will be provided a study chart and an IRB-approved consent for review and signature, and his/her questions will be answered. After a decision is made to enroll into the study, a signature will be obtained from the patient. The original signed consent goes to Medical Records; a copy will be placed in the research record. Patients will not be consented by telephone.

All patients must have a signed informed consent form and an on-study (confirmation of eligibility) form filled out and signed by a participating investigator before entering on study.

Adults unable to give consent are excluded from enrolling in the protocol. However, re-consent may be necessary, and there is a possibility, though unlikely, that subjects could become decisionally impaired. For this reason, and because there is a prospect of direct benefit from

research participation, all subjects \geq age 18 **at the NCI only** will be offered the opportunity to fill in their wishes for research and care, and assign a substitute decision maker on the "NIH Advance Directive for Health Care and Medical Research Participation" form so that another person can make decisions about their medical care in the event that they become incapacitated or cognitively impaired during the course of the study. Note: The PI or AI will contact the NIH Ability to Consent Assessment Team for evaluation. For those subjects that become incapacitated and do not have pre-determined substitute decision maker, the procedures described in MEC Policy 87-4 for appointing a surrogate decision maker for adult subjects who are (a) decisionally impaired, and (b) who do not have a legal guardian or durable power of attorney, will be followed.

